5.2. Drug to be used

B/F/TAF is indicated for treatment of people with HIV-AIDS. Patients enrolled in the study will be switched from a HIV regimen containing abacavir/lamivudine/dolutegravir to B/F/TAF for 24 weeks. In a comparative clinical trial, B/F/TAF was non-inferior to ABC/3TC/DTG in virologic outcomes and showed a significantly lower rate of patient-reported nausea. In Study GS-US-380-1489, a double-blind, multicenter, active-controlled, randomized controlled non-inferiority trial of ABC/3TC/DTG vs B/F/TAF in treatment naïve adults, both regimens were well tolerated. Adverse events leading to study discontinuation were noted in no participants in the bicitegravir, emtricitabine, and tenofovir alafenamide group and 1% of participants in the dolutegravir, abacavir, and lamivudine group. Adverse events related to study drug were less common with bicitegravir, emtricitabine, and tenofovir alafenamide than with dolutegravir, abacavir, and lamivudine (26% [n=82] vs 40% [n=127]), the difference being driven by a higher incidence of drug related nausea in the dolutegravir, abacavir, and lamivudine group (5% [n=17] vs 17% [n=55]; p<0.0001).

5.3. Concomitant medications

Only patients on stable HIV therapies will be included in the study. Because concurrent medications can potentially affect coronary blood flow and flow reserve (e.g., antihypertensive and oral hypoglycemic agents, statins), only patients on stable treatment for hypertension, diabetes and/or dyslipidemia will be included in the study. The following medications will be allowed provided they are neither initiated nor discontinued during the study period:

- Aspirin;
- Angiotensin-converting enzyme inhibitors and/or Angiotensin Receptor Blockers;
- β -blockers;
- HMG –CoA Reductase Inhibitors (statins);
- Nitroglycerin and long-acting nitrates;
- Oral anti-diabetic medications and Insulin;
- Stable hormone replacement therapy

5.4. Procedures

Positron Emission Tomography (PET): Regional and global myocardial blood flow will be assessed using PET imaging. Clinical and research cardiac PET studies are routinely performed at BWH. The PET imaging team at BWH under [name] leadership consist of experienced imaging specialists and have a track record in research studies using PET. [name] has extensive experience in performing these procedures, quantifying myocardial blood flow and flow reserve, has published extensively on this topic, and runs an active core laboratory with experience in multi-center trials using imaging endpoints. PET scans will be performed using a whole body PET/CT scanner. Study participants will be asked to refrain from drinking caffeine-containing beverages and taking theophylline-containing medications for 12 hours before the PET study. Calcium channel blockers, beta blockers, and arterial vasodilators will be withheld for 24 hours prior to the PET scan. Studies will be performed after 4 hours of fasting.

Assessment of myocardial blood flow and coronary flow reserve: Regional myocardial blood flow (MBF) will be measured at rest and during vasodilator-stress with adenosine using ^{13}N -ammonia as the flow tracer. ^{13}N -ammonia is used in clinical and research studies and has been validated for the quantification of myocardial blood flow and coronary flow reserve. After transmission imaging and beginning with the intravenous bolus administration of ^{13}N -ammonia (~20 mCi), list mode images will be acquired for 19 minutes. The patient will then undergo a standard infusion of adenosine (140 mcg/kg/min) for 4 mins or regadenoson bolus injection (0.4 mg). Two mins into the adenosine infusion or one minute after the regadenoson bolus, a second dose of ^{13}N -ammonia will be administered, and PET imaging collected in the same manner. Heart rate, blood pressure, and 12-lead electrocardiogram will be recorded at baseline, every minute during the infusion, and during 5 minutes after completion of the adenosine infusion or regadenoson injection.

Analysis of PET data: Absolute MBF (in ml/g/min) will be computed from the dynamic rest and stress images using commercially available software (Corridor4DM; Ann Arbor, Michigan) and previously validated methods^{33,34}. Automated factor analysis will be used to generate blood pool (arterial input function) and tissue time-activity curves. Regional and global rest and vasodilator-stress MBF will be calculated by fitting the ^{13}N -ammonia time-activity curves to a two-compartment tracer kinetic model as described previously^{33,34}. Per-patient global coronary flow reserve (CFR) will be calculated as the ratio of MBF at peak vasodilator-stress over that at rest for the entire left ventricle. This method for quantitation of MBF is highly reproducible. In the PET core laboratory at BWH, the intra-class correlation coefficient for CFR among four readers is 0.94 (95%CI 0.88-0.98), indicating excellent reproducibility⁵.

Coordination of ancillary study and central imaging analyses. BWH will serve as the coordinating center and central imaging core laboratory for the proposed PET scans in the pilot study. [name] runs a very active core laboratory and, as mentioned above, has extensive experience in managing multi-site imaging trials. In this investigator-initiated study, BWH will sub-contract all clinical centers in the ancillary study.

For the central analysis of the PET images, all imaging data will be stripped of patient identifiers and assigned a trial-specific identifier to maintain compliance with US regulatory requirements regarding protection of patient privacy. Drs. [name] and [name] will organize a bi-monthly teleconference including investigators and research coordinators from each clinical site to monitor, discuss, and troubleshoot recruitment and other issues that may arise during the conduct of the clinical trial.

5.5. Data to be collected and timing of data collection

At each of the study visits, a medical history with symptom assessment, medication review, vital signs, physical exam, and blood samples will be obtained. As described above, additional data from the PET/CT scan as well as EKG assessment will be obtained at baseline and at the end of treatment period. One week after completion of the trial, telephone follow-up will be conducted to assess for any adverse events.

Laboratory analysis: Clinical labs will be collected at the Screening, Baseline, Day 45, and End of Treatment visits as follows:

- Screening: Comprehensive metabolic panel, lipid panel, hs-CRP, HbA1c, CBC, HIV RNA, D-Dimer, Hepatitis B Surface Antigen
- Baseline: hs-troponin and NT-proBNP
- Day 45: Comprehensive metabolic panel, lipid panel, hs-CRP, HbA1c, CBC, HIV RNA, D-Dimer

- End of Treatment: Comprehensive metabolic panel, lipid panel, hs-CRP, HbA1c, CBC, HIV RNA, D-Dimer, hs-troponin, NT-proBNP
- In addition, pregnancy tests will be performed (for women of child-bearing potential) at Screening and before each PET scan.

6. BIostatistical Analysis

6.1. Identification of clinical sites participating in the proposed ancillary study. BWH, MGH, Boston Medical Center and Tufts Medical Center will participate in this pilot study.

Based on the power calculations above and assuming a 20% effect size, the study will need to recruit approximately 30 patients, approximately 10 patients per site. BWH may recruit up to 20 patients. We believe that the proposed study is reasonable and attainable. [name] is an experienced clinical investigator with a successful track record in HIV clinical trials. [name] is a recognized expert in quantitative PET and nuclear cardiology imaging, has published widely on these topics, and has extensive experience in conducting clinical trials using imaging endpoints⁵¹⁻⁵⁴.

6.2. Power Analysis:

The table below shows the sample size needed to reach 85% power for an effect size of 20-30% relative improvement in coronary flow reserve from baseline using a standard deviation of 0.7 at baseline and follow-up and a correlation of 0.7 between baseline and follow-up measurements. Effect sizes were calculated from a baseline mean CFR of 1.74, which is a conservative value derived from our previous measurement of CFR in patients with HIV referred for myocardial perfusion imaging with PET:

Table 2. Power calculation

Effect Size	Mean CFR difference (TAF – Baseline)	SD	Total Sample Size (80% power)	Total Sample Size (85% power)	Total Sample Size (90% power)
20%	0.35	0.7	23	26	30
25%	0.43	0.7	16	18	21
30%	0.51	0.7	12	14	15

Using a total sample size of 30 evaluable patients and a two-tailed alpha of 0.05, there will be 85% power to detect an effect size of 20% relative improvement in coronary flow reserve from baseline, estimating a ~15% attrition rate between time of baseline and final PET. The 20% relative improvement in CFR is the effect size previously demonstrated in statin trials.

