3.2. Source of subjects and recruitment methods

A total of 30 evaluable patients will be required. This will be a collaborative effort between 4 sites in the Boston area: (1) *Brigham and Women's Hospital, BWH* (PI: [name]), (2) *Boston Medical Center* (PI: [name]), (3) *Tufts Medical Center* (PI: [name]), and (4) *Massachusetts General Hospital* (PI: [name]). All patients will be referred for PET imaging to BWH, with BWH serving as the Core Imaging Lab and Data Coordinating Center (PI: [name] [name]).

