9. MONITORING AND QUALITY ASSURANCE

9.1. Safety monitoring

The PI of the study will monitor the overall safety of the study and will report any adverse events to the IRB, per local institutional guidelines. The PI will also monitor this study to ensure that subjects' human rights, safety, and well-being are protected, that the study is properly conducted in adherence to the current protocol, and study data reported by the investigator/subinvestigator are accurate, complete and verifiable with study-related records such as source documents.

Safety data will be obtained at each study visit from the spontaneous reports by patients of adverse events, vital sign monitoring, physical examinations, 12-lead ECGs and clinical laboratory tests. In addition, telephone follow-up will be conducted to assess for any adverse events. All safety data will be reviewed by an HIV physician investigator ([name]).

Patients with unexpected abnormalities on the baseline PET scan will be discussed with the patient's PCP/ID physician to decide whether the patient should participate in this pilot trial. The findings will be discussed with the patient and the patient's primary physician in order to facilitate an appropriate management plan. If a patient is excluded on safety grounds, we do not think that this will affect our ability to determine the effect of B/F/TAF on myocardial blood flow.

The safety of B/F/TAF will be assessed with respect to the following end points: (1) death from any cause, (2) the composite of death from any cause or any cardiovascular hospitalization, (3) frequency of symptomatic documented arrhythmia, (4) serious adverse events related to the study drug and clinically significant laboratory abnormalities.

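### Thirty is both the evaluable number and the number to recruit despite about 15% attrition, and the 85% power quoted for 30 evaluable does not match Table 2

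*Combined protocol and SAP*

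**What the plan says.** Three sections give the sample size.

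- Section 3.2 (Source of subjects and recruitment methods): "A total of 30 evaluable patients will be required". The next sentence names the sites: "This will be a collaborative effort between 4 sites in the Boston area".
- Section 6.1: "the study will need to recruit approximately 30 patients, approximately 10 patients per site", followed by "BWH may recruit up to 20 patients". It lists the same four sites.
- Section 6.2, under Table 2: "Using a total sample size of 30 evaluable patients and a two-tailed alpha of 0.05, there will be 85% power" for a 20% relative improvement. The sentence ends by "estimating a ~15% attrition rate between time of baseline and final PET".

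The 20% row of Table 2 gives 23, 26 and 30 patients for 80%, 85% and 90% power. Section 6.4 makes the primary analysis a paired t-test of the change in coronary flow reserve (CFR). The protocol does not define evaluable.

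**The concern.** A patient without the final PET has no change score and cannot enter the paired test, so the natural meaning of evaluable here is having both scans. If about 15% are lost between scans, the number recruited and the number evaluable cannot both be 30. The power statement has a separate problem: 30 evaluable patients should have the power that Table 2 gives at 30, which is 90%, not the 85% it gives at 26.

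These numbers decide when enrolment closes and whether the planned size was reached. A team that follows Section 6.1 and stops at 30 recruits would almost certainly fall short of the 30 evaluable that Section 3.2 requires. A reader of the final report could not tell from the protocol whether that was a shortfall.

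**Working it through.** **Inputs.** From Section 6.2: SD 0.7 at each visit, correlation 0.7, baseline mean CFR 1.74, 20% effect, two-sided alpha 0.05, attrition about 15%. From Section 6.4: paired t-test.

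**Table 2 first.** SD of change = 0.7 × √(2 × (1 − 0.7)) = 0.542. Difference = 0.20 × 1.74 = 0.348, shown as 0.35 in the table. Exact (noncentral t) sample sizes for the 20% row, using 0.35, are 21, 24 and 28 for 80%, 85% and 90% power, against the table's 23, 26 and 30. Each is within two patients, and the table is on the cautious side. An SD of change of about 0.565 (fitted here, not stated in the protocol) reproduces all nine entries of Table 2. The table is therefore usable, and both scales are shown below.

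**Power at the two candidate numbers of pairs, 20% effect**

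| Pairs | Table 2 | Exact, stated inputs (difference 0.348) | Exact, SD of change 0.565 (difference 0.35) |
|---|---|---|---|
| 26 | 85% | 88.2% | 85.9% |
| 30 | 90% | 92.5% | 90.6% |

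No column gives 85% at 30. Reading 0.7 as the SD of the change itself does not give it either: power at 30 is then 75.4%.

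**Attrition**

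- 30 recruited: 30 × 0.85 = 25.5 pairs. 31 recruited: 31 × 0.85 = 26.35 pairs.
- To obtain 26 pairs: 26 / 0.85 = 30.6, so 31 recruited.
- To obtain 30 pairs: 30 / 0.85 = 35.3, so 36 recruited (35 × 0.85 = 29.75; 36 × 0.85 = 30.6).

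The two readings of the target differ by 36 − 31 = 5 or 36 − 30 = 6 patients.

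**Chance of reaching the number.** Assume each patient is lost independently with probability 0.15. With 30 recruited, the chance of 30 pairs is 0.85^30 = 0.8%. The chance of at least 26 pairs, Table 2's number for 85%, is 52%. On the stated inputs 24 pairs already give 85.3% power, and the chance of at least 24 is 85%. Power averaged over the number of pairs is 87.3% with 30 recruited, 88.4% with 31 and 92.8% with 36.

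**Sites.** 4 × 10 = 40 recruited, or 40 × 0.85 = 34 pairs, which matches neither 30 nor 36. A total of 30 is 30 / 4 = 7.5 per site on average, and 31 is 31 / 4 = 7.75.

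**The case against.** The best defence is that the power sentence carries its own attrition allowance. Applied to 30, that allowance leaves 25.5, and Table 2 gives 85% at 26. If 30 already meant patients with both scans, there would be no reason to mention attrition there. On this reading 30 is the enrolled number, or the number with an accepted baseline scan. The second meaning has some footing in Section 9.1, where an unexpected baseline PET finding can lead to a patient not taking part. Sections 3.2, 6.1, 6.2 and Table 2 then agree to within rounding.

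Most of this stands as an account of what was probably intended, and the power claim survives on it. It does not remove the inconsistency. It requires evaluable to mean something the protocol never states, in two places, for an endpoint that needs both scans.

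Two further points are fair. The 52% chance of 26 pairs uses Table 2's cautious threshold and should not be read as a 48% risk of inadequate power. And the per-site figure is approximate, with the lead site allowed up to 20, so uneven recruitment was foreseen. Neither point makes four sites at about 10 each add up to about 30.

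**Conclusion.** The concern holds. The sample size is stated inconsistently: 30 is the evaluable number in Sections 3.2 and 6.2 and the number to recruit in Section 6.1, and with about 15% attrition it cannot be both. Read literally, 85% power at 30 evaluable also contradicts Table 2, which gives 90% there.

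The effect on inference is small. Power for the 20% effect is about 85% or better at 26 pairs and 90% or better at 30, and the analysis method and type I error do not change. What is left unsettled is the recruitment target: 30 to 31 or 36. This rests on evaluable meaning both PET scans available, as the paired test requires, and on the protocol's own attrition, SD and correlation. The probabilities of reaching a given number of pairs also assume independent loss. It should be fixed, but it does not threaten the trial.

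**What to change.** Give the enrolled and evaluable numbers separately, in identical terms, in Section 3.2 (Source of subjects), Section 6.1 and Section 6.2, and define evaluable as having both PET scans available for the paired test. Suggested wording: *About 30 to 31 patients will be enrolled. With about 15% attrition, about 26 will have both PET scans, which gives about 85% power for a 20% relative improvement in CFR (Table 2).*

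Replace the per-site figure with one that fits four sites and this total, for example an average of 7 to 8 per site, keeping the lead site's allowance of up to 20.

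The cost is a wording amendment, with at most one patient beyond the roughly 30 that Section 6.1 already plans to recruit.

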6.3. Study endpoints

Primary Endpoint: Change (from baseline) in coronary flow reserve, as measured by PET imaging at 24 weeks post medication switch.

Secondary Endpoints:

- (1) Change (from baseline) in peak-stress global myocardial blood flow (in mL/min/g) at 24 weeks after initiation of B/FTAF;

- (2) Change (from baseline) in peak-stress global coronary vascular resistance (in mm Hg/mL/min/g) at 24 weeks after initiation of B/FTAF;
- (3) Change in serum biomarkers of inflammation (hs-CRP, IL-6, sCD163 and sCD14), myocyte injury and strain (hs Troponin, NT-proBNP) at 24 weeks after initiation of B/F/TAF.

6.4. Statistical methods

To test *the central hypothesis*, that reducing endothelial cell activation and dysfunction by substituting B/F/TAF for ABC/3TC/DTG will quantitatively improve coronary flow reserve as measured by PET over 24 weeks, we will perform a paired t-test to assess the Δ CFR between baseline and follow-up for each subject.

If a significant change in CFR after the switch is observed, we will perform secondary analyses of association between other markers of inflammation also implicated in atherosclerosis (hs-CRP, IL-6, sCD163 and sCD14) with Δ CFR. Significance of associations with other inflammatory markers and Δ CFR will be adjusted using the Bonferroni correction.

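### Plain Bonferroni for the four marker associations is valid, but Holm gives the same familywise guarantee and can only add rejections; a small, nearly free gain in a secondary, gated analysis

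*Combined protocol and SAP*

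**What the plan says.** Section 6.4 first specifies a paired t-test of the change in CFR. The marker work is conditional on its result: "If a significant change in CFR after the switch is observed, we will perform secondary analyses of association". Four markers are named: hs-CRP, IL-6, sCD163 and sCD14. On multiplicity the text says that the significance of their associations with the change in CFR "will be adjusted using the Bonferroni correction". No step-down or other sequential method is mentioned.

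For these tests section 6.4 gives no alpha, no sidedness, no association method and no power. The only alpha in the plan is in section 6.2, for the primary comparison: "Using a total sample size of 30 evaluable patients and a two-tailed alpha of 0.05". The same paragraph expects about 15% attrition between the two scans.

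The secondary endpoints in sections 2.3 and 6.3 include the change in the markers. The association of markers with the change in CFR is not a listed endpoint.

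**The concern.** Plain Bonferroni holds each of the four p-values to 0.05/4 = 0.0125, whatever the other three show. Holm relaxes the threshold after each rejection and keeps the same familywise guarantee. Where several markers are truly associated with the change in CFR, plain Bonferroni can therefore miss the second, third or fourth when Holm would not.

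The sample is small, so the threshold is demanding. The plan's rationale treats inflammation as a common driver of coronary vascular dysfunction, which makes joint association of several markers plausible, though section 6.4 predicts no number. At stake is which markers are reported as tracking the change in CFR. The primary endpoint, its test and the sample size are not touched.

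**Working it through.** **Inputs from the documents.** Four markers and the Bonferroni correction (section 6.4). Sample size 30, or 30 × 0.85 = 25.5, about 26, if the attrition is taken from 30 (section 6.2). The text does not settle whether 30 is before or after attrition, so both are used.

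**The plan's own figure.** There is none for the marker tests. The nearest is the primary sample size in Table 2: 23, 26 and 30 patients for 80%, 85% and 90% power at a difference of 0.35. Its inputs are "using a standard deviation of 0.7 at baseline and follow-up and a correlation of 0.7 between baseline and follow-up measurements", and "Effect sizes were calculated from a baseline mean CFR of 1.74". The SD of the change is √(2 × 0.7² × (1 − 0.7)) = √0.294 = 0.542. A two-sided paired t-test at 0.05 then needs 21, 24 and 28 patients, each within 2 of the table. So 26 to 30 is a fair range for the marker analysis.

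**Thresholds.** With m = 4 and familywise alpha 0.05:
- Bonferroni: 0.05/4 = 0.0125 for every marker.
- Holm, from smallest to largest p-value, stopping at the first failure: 0.05/4 = 0.0125, 0.05/3 = 0.0167, 0.05/2 = 0.025, 0.05/1 = 0.05.

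No Holm threshold is below 0.0125, so Holm rejects whatever Bonferroni rejects.

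**Why the guarantee is the same.** Suppose m₀ of the m nulls are true. When Holm first reaches a true null, at most m − m₀ hypotheses have been rejected, so the threshold is at most 0.05/m₀. The chance that any of m₀ null p-values falls below 0.05/m₀ is at most 0.05, whatever their dependence.

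**How demanding 0.0125 is.** For a Pearson correlation the critical value is |r| = t/√(t² + n − 2), with t the two-sided 0.0125 point on n − 2 degrees of freedom. This gives 0.450 at n = 30 and 0.483 at n = 26.

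**Power.** Assumptions, none of them in the documents for these tests: two-sided familywise 0.05, Pearson tests on multivariate normal data, correlation 0.3 between markers, and equal true correlation r with the change in CFR. The figures are simulated and apply once the analysis is run; they are not multiplied by the chance that the primary test is significant. Power per truly associated marker, all four true:

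| n | r | Bonferroni | Holm |
|---|---|---|---|
| 26 | 0.3 | 15% | 18% |
| 26 | 0.4 | 32% | 39% |
| 26 | 0.5 | 57% | 67% |
| 30 | 0.3 | 19% | 22% |
| 30 | 0.4 | 39% | 46% |
| 30 | 0.5 | 65% | 76% |

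Fewer true markers, n = 30, r = 0.5:
- three true: 65.0% to 70.8%
- two true: 64.7% to 67.3%
- one true: 64.7% to 64.8%

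With two true and r = 0.3 the gain is under one point: 18.7% to 19.6% at n = 30 and 15.4% to 16.1% at n = 26.

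**At least one marker.** The smallest p-value faces 0.0125 under both methods, so both reject at least one hypothesis in exactly the same data sets. With all four true at r = 0.5 and n = 30, the figure is 96.5% for both.

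**Familywise error.** With no true association it is the same for both methods: 4.6% at n = 26 and 4.9% at n = 30. With some markers true, Holm uses error that Bonferroni leaves unspent, but in these runs it reached at most 4.3%.

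**Sensitivity to dependence.** With n = 26, r = 0.5 and all four true, independent marker residuals give 56.5% to 67.1%, and a residual correlation of 0.5 gives 56.6% to 66.0%.

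**The case against.** The strongest reply is that nothing here is wrong. Bonferroni is valid, prespecified, simple and conservative. The analysis is secondary, runs only after a significant primary result, and belongs to an uncontrolled single-arm pilot. All of that stands, and a reader who inferred that the plan has a multiplicity error would be mistaken.

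A reader might also infer that the plan gives up power generally. It does not. Only the second and later rejections can gain. If the question is whether any marker tracks the change in CFR, the two methods give the same answer.

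The most striking contrast is the chance of finding all four markers, which rises from 24% to 49% at n = 30 and r = 0.5. It should not be read as the typical gain. Four markers at r = 0.5 with mutual correlation 0.3 would jointly explain 4 × 0.25/(1 + 3 × 0.3) = 1/1.9, about 53% of the variance in the change in CFR. That is optimistic, and nothing in the documents supports it. At r = 0.3 the same formula gives 0.36/1.9, about 19%, and the gain per marker is only about 3 points, from a low base.

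The last reply is that Bonferroni has simple matching simultaneous intervals. That is true, but section 6.4 plans none, so nothing planned would be lost.

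**Conclusion.** The point holds as a cheap improvement of the lowest severity. That Holm keeps the 5% familywise guarantee and never rejects less is a mathematical fact and rests on no assumption about the data. The size of the gain does rest on assumptions: the 0.05 two-sided familywise level, Pearson tests, the correlation between markers, and the number and strength of true associations.

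Across r from 0.3 to 0.5 and 26 to 30 patients, the gain per marker is about 3 to 11 points if all four are truly associated, about 1 to 3 points if two are, and about zero if one is. The documents do not support reading this as a remedy for the sample size: with r = 0.3, power per marker stays at 22% or below under either method.

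**What to change.** Before the association data are examined, replace the reference to Bonferroni in section 6.4 with: *the Holm step-down procedure across the four markers (familywise two-sided alpha 0.05)*. Report Holm-adjusted p-values, with 95% confidence intervals labelled as unadjusted. This also puts the family and its alpha on record, which section 6.4 does not now do.

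The cost is a few words and no extra patients or data. The one downside is that simultaneous intervals matching Holm are less simple to construct. With unadjusted intervals, an interval may exclude zero while its adjusted test is not significant, so the label matters.
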